Parents of eligible infants will be approached during their post-partum hospitalization or in the NICU at LUMC. A research team member will provide details regarding the study purpose, procedures, and answer questions. Parents will be provided with a study brochure. If parents request additional time to make their decision, we will request a phone number and ask permission to follow-up. If parents agree to have their infant participate, a written informed consent and authorization to use and disclose the PHI will be obtained. Parents will receive a copy of their signed informed consent and authorization to use and disclose the PHI. A copy of the informed consent form will be uploaded to the infant's electronic medical record. The original signed consent will be stored in a locked cabinet at LUC CTRE (Maywood, IL). Infant's participation in the study will end after the phone/Zoom interview at 2 months CA. We will provide a \$50 incentive e-gift card at NICU discharge and a \$50 incentive e-gift card at the completion of the post-discharge follow-up, a total of \$100 e-gift card. Premature infants, by virtue of their age, are unable to give consent or assent, and therefore, will not give assent or participate in the informed consent process.

iv. Randomization Procedures

Randomization is controlled by using two computer-generated lists of random numbers that are corresponded to each group: Group 1 (M-MILK) and Group 2 (attention control), balanced so that 1/2 of the infants are in each group. The lists are retained. The random numbers will be printed in order on small cards stated as Group 1 or Group 2. The cards will be placed in envelopes and placed in order in a box. Prior to approaching parents for recruitment, we will open the first envelope in the box to obtain the group assignment. We will request parents to not disclose their group assignment with other parents in the NICU. The research team

members, staff nurses, and parents cannot be blinded to the treatment condition. The research team members need to know which intervention to provide. Staff nurses provide direct care to infants. The two groups are described in the consent form as required by LUC Institutional Review Board.

v. Study Intervention

1. MMILK Intervention

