For infants in the attention control group, standard of care will be provided, including hands-on care by their nurses, diapering, swaddling, feeding, etc. After assessment and initial cares are completed, infants are tucked and nested with boundaries to support comfort, security, and flexion. The infants' hands are placed by their faces to encourage self-soothing, mouthing, and sucking. We will provide parents with two scent hearts to wear

and bring back to place near the infant's face. Parents perform routine care such as taking temperature, bathing, changing diapers, reading, feeding, and holding hands. Parents will have access to educational materials regarding preterm infant care such as Your Guide to Neonatal Intensive Care Unit and Breastfeeding in the NICU. Parents will receive an automatic daily text in the morning with a link to report their daily activities with infants when they visit the NICU. Parents in the attention control group will not have access to the M-MILK content.

vi. Study Assessments and Activities

1. Measures

Table 1. Concepts, Measures, and Operational Definitions

Concepts	Operational Definitions	Data Source & Time
Parent characteristics	Parent characteristics will include both mother and father as applicable. We will collect race/ethnicity, education, age at delivery, household income, number of children, number of children under 24 months, and social determinants of health (i.e., physical activity, financial resource strain, housing stability, transportation needs, food insecurity, stress, social connections, intimate partner violence, and alcohol use)	T0 EPIC & self-report
Maternal postpartum depressive symptoms	Maternal postpartum depressive symptoms are assessed by the Edinburgh Postnatal Depression Scale (EPDS). ³² The EPDS consists of 10 short statements. A mother checks off one of four possible answers that is closest to how she has felt during the past week. Responses are scored 0, 1, 2 and 3 based on the seriousness of the symptom. Items 3, 5 to 10 are reverse scored (i.e., 3, 2, 1, and 0). The total score is calculated by adding together the scores for each of the 10 items. Mothers scoring above 12 or 13 are likely to be suffering from depression and should seek medical attention. The pooled sensitivity and specificity of the EPDS were 0.81 and 0.87, respectively, with summary receiver operating characteristic curve of 0.90. ³³	T0, T3, T4 EPDS

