Charges and costs of care	Healthcare use and associated charges and costs of the NICU hospitalization and 2 months CA care will be extracted from LUMC's electronic health and billing records. For infants receiving care outside LUMC 2 months CA, we will ask the parents about the extent and types of healthcare received outside LUMC. We will evaluate healthcare use, costs, and charges between the M-MILK and control groups. We will also describe the extent and types of healthcare use 2 months CA for infants receiving care outside LUMC at discharge. In the R01 trial, we will use activity-based costing approach to calculate the time and resources costs of delivering the M-MILK intervention by nurses and parents (which may not be fully reflected in the health system billing records), and query NICU hospitalization and 2 months CA healthcare use, charges, and costs to calculate total benefits and costs of M-MILK Intervention vs. control group.	T3 & T4
M-MILK Acceptability Questionnaire	The M-MILK Acceptability Questionnaire will be completed by parents at discharge. The nurses will complete the M-MILK Acceptability Questionnaire at the end of the entire study.	T3 M-MILK Acceptability Questionnaire

Note. EPIC = electronic medical record; GA = gestational age; PMA = postmenstrual age; CA = corrected age; Ongoing = throughout hospitalization from enrollment to discharge; T0 = baseline; T1 = 34 weeks PMA; T2 = oral feeding initiation; T3 = discharge; T4 = 2 months CA

ii. Procedures

Figure 2. After informed consent is obtained, infants will be randomized into: Group 1 (M-MILK) and Group 2 (attention control). All data collection will be conducted in the same manner and at the planned time points for both groups. For all infants, we will collect infant characteristics, NISS, and family NICU activities daily ongoing from EPIC and self-report. All parents will receive an automatic daily text in the morning with a link to report their daily activities with infants when they come to the NICU. All parents are signing up for daily texts for up to 20 weeks to complete daily activities report every day during their participation. All parents will also receive a weekly phone call from a research nurse from enrollment until discharge. M-MILK is primarily implemented by nurses or parents. **At baseline (T0)**, we will conduct the EPDS assessment, and collect parent characteristics,

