buccal swab and fecal samples. For infants in the M-MILK group, the clinical team will place an order in EPIC for M-MILK to be provided starting on day 3 of life according to the M-MILK protocol. We will also schedule an in-person 30-minute M-MILK training session with parents in the M-MILK group, within 1 week of enrollment, provided by a research nurse. Parents in the M-MILK group are encouraged and supported to provide M-MILK when appropriate with the nurse's supervision. **At 34 weeks PMA (T1)**, we will collect PBQ, buccal swab and fecal samples. **At oral feeding initiation (T2)**, we will collect the EFS, and NCAST-Feeding video recording. Day of initiation of oral feeding is defined as the first of at least two consecutive days when the infant is able to orally consume $\geq 10\%$ of their prescribed feedings. Infants will be fed by nurses, speech therapist, or PI. We will implement the same feeding protocol, e.g., side-lying and swaddling during feeding. **During the week of planned discharge (T3)**, we will conduct EPDS, PSS: NICU, PDR, PBQ, Pumping and Breastfeeding, NMI, NAPI, and EFS assessments. We will collect NCAST-Feeding video recording, buccal swab and fecal samples. For the NCAST-Feeding video recording, both parents and infants will be recorded. Parents will also complete the M-MILK Acceptability Questionnaire at T3. For EFS and NAPI assessments, we will video record the assessments, when possible, to obtain videos for inter-rater reliability. **At 2 months CA (T4)**, we will send parents the fecal and buccal sample collection kits via USPS mail service. We will also conduct a phone/Zoom interview to complete the EPDS, PBQ, ASQ-3, and NeoEAT assessments. During the phone/Zoom interview, we will also provide parents instructions on how to collect buccal and fecal samples and securely send them back to us.

VIII. Safety Monitoring Plan

a. Potential Risk

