1. Risks Related to Study Procedure

During the study, if an infant becomes clinically unstable and/or develops new diagnosis, and no longer meet the inclusion criteria, we will remove the infant from the research protocol. The M-MILK intervention's safety has been demonstrated in infants as young as 22 weeks GA. According to the M-MILK protocol, nurses or parents will carefully observe infants' cues and responses during the M-MILK intervention and stop the administration if infants do not engage or exhibit any signs of distress. When collecting the buccal swab samples and administering NAPI, we will make every effort to be as gentle as possible and omit any item(s) that may be causing discomfort to infants. If parents report a score of 12 or above on the EPDS, we will make referrals to the NICU Social Worker. If parents report "yes, quite often" or "sometimes" to the question "the thought of harming myself has occurred to me" on the EPDS, we will refer the parent to the local Emergency Department immediately. For the PBQ, parents scoring ≥ 26 , (indicating risk of general bonding disorders) or ≥ 40 (indicating risk of severe bonding disturbances) should seek medical attention. For the PBQ, parents scoring "rarely", "sometimes", "quite often", "very often", or "always" for item 18 "I have done harmful things to my baby" or item 24 "I feel like hurting my baby" indicates risk of child abuse. In this case, it is our responsibility to report it to the state's child protective agency. If the infant is in immediate danger, the research staff will be instructed to inform the parents of their immediate concerns for the infant's safety, report the incident using a cellular phone, and call 911 until appropriate officials arrive. The PI will be informed of the family's condition and always be available by phone or in person for consultation and instruction. As part of the training of our research team, the team will review content related to reporting of child neglect and abuse.

2. Risks related to Data Confidentiality

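### One non-zero answer to the EPDS self-harm question has no stated response when the total is below 12, and at T4 no later assessment could catch it

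*Combined protocol and SAP*

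**What the plan says.** Table 1 (section VII.a.vi.1, maternal postpartum depressive symptoms) describes the instrument: "A mother checks off one of four possible answers that is closest to how she has felt during the past week". It continues: "Responses are scored 0, 1, 2 and 3 based on the seriousness of the symptom". The total is the sum of ten items, and the scale is given at T0, T3 and T4.

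Section VIII.b.ii.1 (Risks Related to Study Procedure) gives two actions:

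- On the total score: "If parents report a score of 12 or above on the EPDS, we will make referrals to the NICU Social Worker".
- On the self-harm question: the rule opens "If parents report 'yes, quite often' or 'sometimes' to the question 'the thought of harming myself has occurred to me' on the EPDS", and the action is immediate referral to the local Emergency Department.

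Three other statements bear on whether a missed answer could be noticed later:

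- The Procedures text under section VII.a.vi says "All parents will also receive a weekly phone call from a research nurse from enrollment until discharge".
- For T4 the same text says "We will also conduct a phone/Zoom interview to complete the EPDS, PBQ, ASQ-3, and NeoEAT assessments".
- Recruitment Procedures (VII.a.iii) says of the infant that "participation in the study will end after the phone/Zoom interview at 2 months CA".

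**The concern.** A question about thoughts of self-harm needs a stated response for every affirmative answer, because a mother may endorse it while scoring low on the other items. Here the item rule covers some affirmative answers, and the rest are left to the total score. A mother who gives the uncovered answer with a total below 12 has disclosed such a thought to the study, and the protocol, followed exactly, asks nobody to act.

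During the NICU stay, other contact might bring the matter out by chance. At T4 the answer is given remotely, in the last scheduled interview, so nothing later in the study would reveal it.

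**Working it through.** No sample size, power or error rate is involved. The check is whether the two rules together cover every non-zero answer.

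**Inputs**

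- Four answers per item, scored 0, 1, 2 and 3 (Table 1). Some items are reverse scored, which changes the order of the scores but not the set.
- Two self-harm answers trigger Emergency Department referral (VIII.b.ii.1).
- The total-score trigger is 12 or above (VIII.b.ii.1).
- Three EPDS time points: T0, T3 and T4 (Table 1).
- N = 12 in the design and sample sections; N = 20 in the abstract.

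**Step 1: answers covered.** Non-zero answers: 4 − 1 = 3. Named in the rule: 2. Left without an item-level response: 3 − 2 = 1. This requires that neither named answer scores 0; both are plainly affirmative.

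**Step 2: totals at which nothing applies.** Let *s* be the score of the unnamed answer and *R* the sum of the other nine items. Neither rule applies when *s* + *R* ≤ 11.

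| *s* | *R* | Totals with no stated action |
|---|---|---|
| 1 | 0 to 10 | 1 to 11 |
| 2 | 0 to 9 | 2 to 11 |
| 3 | 0 to 8 | 3 to 11 |

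The protocol does not print the unnamed answers or their scores. Scoring follows seriousness and the named answers include the strongest-sounding one, so *s* = 1 is the likely row. The other rows show that the gap does not depend on that inference.

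**Step 3: does other text close it?**

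- The remark in Table 1, "Mothers scoring above 12 or 13 are likely to be suffering from depression and should seek medical attention", does not reach totals below 12.
- The bonding-questionnaire (PBQ) rules concern bonding and harm to the infant. The sentence on the principal investigator's availability belongs to that child-protection text.
- The weekly nurse call is not described as a response to EPDS answers, and it stops at discharge.
- After the T4 interview, the only study contact described is the return of mailed sample kits, which is not an assessment.

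**Step 4: comparison within the same paragraph.** PBQ items 18 and 24 have six answers. The protocol acts on every one except *never*, whatever the total: 5 of 5 affirmative answers. For maternal self-harm it acts at item level on 2 of 3.

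**Step 5: exposure.** At most 12 × 3 = 36 EPDS completions, or 20 × 3 = 60 under the abstract's N, assuming one mother per infant and no attrition. If only half returned at T4, the protocol's own threshold for feasible follow-up, the first figure would be 12 + 12 + 6 = 30. These are opportunities for the gap to arise, not affected mothers.

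**The case against.** The best defence is that the tiering is deliberate clinical judgement. The two named answers get the most urgent response, and a mother giving the weaker answer is still referred once her total reaches 12. What remains is, by inference, the mildest affirmative answer in a mother below the depression cut-off. The rule is silent there; it does not forbid follow-up, and a research nurse who heard the answer might well act. In a sample this small the number affected may be zero.

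Part of this stands. Reserving immediate Emergency Department referral for the two named answers is reasonable and should be kept. The wording of the omitted answer is inferred, and no prevalence can be given.

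It does not close the gap. Reliance on individual judgement is what a written safety rule is meant to replace, and a total-score cut-off is not a response to a self-harm answer. The protocol also accepts elsewhere in the same paragraph that a single harm item may need action at any affirmative level. The two settings differ, since the PBQ rule carries a reporting duty. That may justify a milder response here, but not the absence of one.

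**Conclusion.** The concern holds. One of the three non-zero self-harm answers has no stated response at totals below 12: totals 1 to 11 if it scores 1, and a slightly narrower range otherwise. The gap is present at all three EPDS time points and matters most at T4.

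The conclusion rests on the four-answer, 0-to-3 scoring in Table 1 and on both named answers being non-zero. It refers to the protocol as published; pages removed from the public copy, such as the consent form, were not available. It should be fixed for participant safety. It has no bearing on the aims, the variability estimates or the feasibility criteria.

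**What to change.** Amend section VIII.b.ii.1 so that any non-zero answer to the EPDS self-harm question triggers action at any total. Suggested content:

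- Keep immediate Emergency Department referral for the two answers now named.
- For the remaining non-zero answer, require at least a same-day referral to the NICU Social Worker or a same-day safety assessment by a clinician. Site clinicians should set the content.
- State that the rule applies at T0, T3 and T4, and that the item is read on the day it is completed.
- For T4, say who acts and how when the answer comes by phone or Zoom. The infant has left the NICU by then, so a clinician assessment is likely to fit better than a NICU Social Worker referral.

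A small tidy-up at the same time: align the Table 1 cut-off wording with the operative 12 or above. That mismatch does not cause any mother to be missed.

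The cost is about one sentence for the added tier, a short T4 instruction, a REDCap flag on one item and possibly a few more follow-up conversations among 12 families. No sample size, outcome or analysis changes.

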More than 60,000 infants are born between 22 to 32 weeks gestation age (very or extremely premature) annually in the US. Approximately 11% of them develop comorbidities, i.e., oral feeding difficulty, failure to thrive, delayed neurodevelopment, and maladapted parent-infant interaction. As part of the Neonatal Intensive Care Unit (NICU) hospitalization, very and extremely preterm infants inevitably endure early life toxic stress, e.g., parental separation, painful procedures, sleep fragmentation, harmful hospital organisms, and antibiotic therapy, without adequate protective buffers. Early life toxic stress results in adverse epigenetic modifications of glucocorticoid-related genes (DNA methylation of NR3C1 and HSD11B2) and dysbiosis (altered gut microbiome), both impairing neurodevelopment. These adversities further exacerbate the risk of comorbidities and inappropriate brain development during sensitive periods of neuroplasticity. Evidence suggests adverse epigenetic modifications and dysbiosis may set a life-long trajectory of risk for chronic health conditions, i.e., mental health disorders, cardiometabolic and immunologic diseases. Hence, it is a clinical and scientific priority to test an early NICU intervention to attenuate stress-related adverse epigenetic modifications and dysbiosis. Prior research has paved the way for a potential early NICU intervention as follows. Human milk influences the structure and relative abundance of healthy gut bacteria, i.e., short-chain fatty acid (SCFA)- and lactate-producing bacteria (e.g., *Bifidobacterium* and *Lactobacillus*), and neurodevelopment. Maternal nurturing, e.g., licking and grooming (in rodents), and breastfeeding and touch (in humans), promotes neurodevelopment, reduces stress, and reverses stress-related epigenetic modifications. Building on what is known, the multisensory early oral administration of human milk (M-MILK) intervention by nurses or parents is designed to provide an enjoyable and nurturing experience for infants, through a safe and consistent infant-guided provision of human milk droplets, given orally as early as 22 weeks postmenstrual age. M-MILK is implemented after every hands-on care and during the beginning of a full gavage feeding. The objective of our planned NIH R01 randomized controlled trial is to examine the efficacy of M-MILK from birth to 2 months corrected age, and the mechanisms whereby this may occur. We propose the M-MILK pilot study (N = 20): a 2-group, 10 per group, parallel design, and longitudinal randomized controlled trial in preterm infants who are born between 22 to 33 weeks gestational age. M-MILK will begin on day 3 of life. We will measure outcomes using validated methodologies: maternal postpartum depressive symptoms via the Edinburgh Postnatal Depression Scale, parent stress via the Parental Stressor Scale: NICU, parent discharge readiness via the Screening and Multi-disciplinary Risk Assessment Scale & Parent Activation Scale, neurodevelopment via the Neurobehavioral Assessment of the Preterm Infants and Ages & Stages Questionnaire-3, oral feeding skills via the Early Feeding Skills Assessment and NeoEAT, parent-infant interaction during feeding via the Nursing Child Assessment Satellite Training-Feeding Scale and Postpartum Bonding Questionnaire, DNA methylation of NR3C1 and HSD11B2 via buccal samples, and gut microbiome via fecal samples. Outcomes will be measured at baseline, 34 weeks postmenstrual age, discharge, and 2 months corrected age. The aims of this pilot study are to (1) determine the feasibility and acceptability of the M-MILK intervention by nurses and parents, (2) determine the feasibility of recruitment and retention, (3) obtain variability data for sample size estimation, and (4) evaluate the charges and costs of the NICU hospitalization and 2 months CA care between the M-MILK and control groups. M-MILK will be considered feasible if M-MILK is implemented by nurses or parents after every hands-on care and during the beginning of a full gavage feeding at least 90% of the time. The M-MILK acceptability by nurses and parents will be determined via M-MILK Acceptability Questionnaire. Recruitment and retention will be considered feasible if at least 50% of infants approached for participation enrolled, 90% of infants completed all inpatient data collection, and at least 50% of infants completed post-discharge follow-ups. This pilot study will inform our R01 application regarding the feasibility and acceptability of M-MILK and sample size estimation.

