The aims of this pilot study are to (1) determine the feasibility and acceptability of the M-MILK intervention by nurses and parents, (2) determine the feasibility of recruitment and retention, (3) obtain variability data for sample size estimation, and (4) evaluate the charges and costs of the NICU hospitalization and 2 months CA care between the M-MILK and control groups. M-MILK will be considered feasible if M-MILK is implemented by nurses or parents after every hands-on care and during the beginning of a full gavage feeding at least 90% of the time. The M-MILK acceptability by nurses and parents will be determined via M-MILK Acceptability Questionnaire. Recruitment and retention will be considered feasible if at least 50% of infants approached for participation enrolled, 90% of infants completed all inpatient data collection, and at least 50% of infants completed post-discharge follow-ups.

V. Administrative Organization

Participants will be enrolled in the Neonatal Intensive Care Unit (NICU) at Loyola University Medical Center (LUMC) (Maywood, IL). The inpatient components of the study protocol will be conducted in the NICU at LUMC. The post-discharge follow-up components of the study protocol will be conducted via phone/zoom interview. Data storage and management will be carried out via REDCap (version 10.4.0, Vanderbilt University) and a secured research network drive, hosted by the Loyola University Chicago (Maywood, IL).

Upon sample collection, buccal swab and fecal samples will be labeled only with study ID numbers and collection date, and stored in a locked cabinet in a locked laboratory at Loyola University Chicago (LUC) Center for Translational Research and Education (CTRE). All samples will be stored at room temperature. Quarterly, the buccal swab samples and fecal samples will be securely transported in a biospecimen transfer container (Saf T Pak, Austell, GA) via car to Rush University Medical Center Genomics and Microbiome Core Facility (Rush) (Chicago, IL) for processing and analyses. A Service Agreement between LUC and Rush will be submitted through LUC Research Portal.

VI. Study Design

a. Design

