The M-MILK pilot study ($N = 12$) is a 2-group, 6 per group, parallel design, and longitudinal randomized controlled trial. We will recruit preterm infants who are born between 22 to 33 weeks gestational age. We will compare the outcomes between the M-MILK and attention control groups. Infants will be enrolled into the study as soon as possible after they are admitted to the NICU. If infants are in the M-MILK group, M-MILK will begin on day 3 of life after every hands-on care and during the beginning of a full gavage feeding. We will measure outcomes using validated methodologies at baseline (enrollment), 34 weeks PMA, discharge, and 2 months CA.

b. Setting

The M-MILK pilot study will be conducted in a level III NICU at LUMC (Maywood, IL). The hospital provides care to families with diverse racial, ethnic, and socioeconomic backgrounds. The nursing staff are predominantly registered nurses and advanced nurse practitioners, and the physicians are board certified

neonatologists. Infants are fed using mother's own milk, donor milk, and/or formula. However, we will only include infants who receive mother's own milk or donor's milk.

c. Sample

We will enroll 12 preterm infants (6 per group). Anticipated a 40% attrition rate, we expect the final sample size to be 12 preterm infants. Estimates of average values and variability of continuous measures are acceptable at this sample size using the "rule of 12" as recommended.³¹

VII. Study Procedures

a. Subject Selection Procedures

i. Inclusion/Exclusion Criteria

Inclusion criteria

- Born between 22 to 33 weeks gestational age
- Mother is pumping and infant is receiving mother's own milk and/or donor's milk to be in the intervention group.

Exclusion criteria

- Congenital abnormalities in the digestive, e.g., clef lip and palate, omphalocele
- Necrotizing enterocolitis
- Congenital heart disease that requires surgery

ii. Screening procedures

After infants are admitted to the NICU, we will review their electronic medical records to screen for eligible infants according to the inclusion and exclusion criteria. Once an infant is enrolled into the study, the screening period continues until NICU discharge. The infant will be classified as screen failed and excluded if he/she develops any of the exclusion criteria.

iii. Recruitment Procedures

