Strict confidentiality of data files will be maintained. Data management will be facilitated using REDCap. SAS (v 9.4) will be used for all statistical procedures and analyses. Levels of missingness, variable distributions, and outliers will be examined throughout data collection for quality assurance as well as prior to statistical modeling. We will calculate descriptive statistics for all variables of interest to describe the variability of study variables, and conduct sample size estimation for the planned R01 application. Comparisons will be made using an intent-to-treat approach with participants analyzed in the groups to which they were randomized. Feasibility will be assessed with respect to enrollment, adherence, acceptability, and safety. We will calculate the percentage of infants who (1) were eligible, approached, consented, enrolled, and randomized over the recruitment period, (2) were retained for the duration of the study, (3) completed all inpatient data collection, and (4) completed post-discharge follow-ups. To determine the adherence of M-MILK, we will calculate the daily numbers of completed M-MILK and the daily numbers of expected M-MILK implementation (numbers of hands-on care episodes before full gavage feedings) to obtain the daily percentage of M-MILK completion. We will summarize findings from M-MILK Acceptability Questionnaire by nurses and parents. We will also summarize findings from M-MILK EPIC charting regarding infant's responses and any adverse events to monitor for the safety of M-MILK.

X. Study Timeline

Table 2. The proposed pilot study will require 1 year to complete. During the first 3 months, we will hire and train the team members. We anticipate enrolling 2 infants per month for 9 months. An additional 3 months will be required to complete the intervention and collect study data. Data entry and analyses will be ongoing. We will spend 6 months to complete data analyses. An additional 6 months will be needed to prepare the final report and disseminations.

Table 2. Study Timeline

Activity/Month	Month 1-3	Month 3-12	Month 12-15	Month 15-21	Month 21-27
Preparation & Staff Training	X				
Recruitment & Enrollment		X			
Data Collection		X	X		
Data Entry & Analyses		X	X	X	
Final Reports & Dissemination				X	X

XIII. Literature Cited

1. Barfield WD. Public Health Implications of Very Preterm Birth. *Clin Perinatol*. Sep 2018;45(3):565-577.

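### Section IX gives gestational age at birth no stated role in the between-arm comparisons or in the variability estimates meant to size the R01

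*Combined protocol and SAP*

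**What the plan says.** Eligibility (Section VII.a.i) covers infants "born between 22 to 33 weeks gestational age". Section VI.c states "We will enroll 12 preterm infants (6 per group"), then "Anticipated a 40% attrition rate, we expect the final sample size to be 12 preterm infants", and justifies the number by a rule of thumb: "Estimates of average values and variability of continuous measures are acceptable at this sample size". The opening abstract gives a different size: "We propose the M-MILK pilot study (N = 20): a 2-group, 10 per group, parallel design".

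Section VII.a.iv says "Randomization is controlled by using two computer-generated lists of random numbers", balanced 1:1, and describes no stratification by GA. Table 1 lists GA at birth among the infant characteristics and notes that Early Feeding Skills (EFS) scores correlate with GA, without giving a size.

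Section IX says "We will calculate descriptive statistics for all variables of interest to describe the variability of study variables, and conduct sample size estimation"; this estimation is meant to serve the R01. It adds comparisons by intention to treat and refers to statistical modelling without naming a model or covariate. The only covariate language is in Table 1, where a PERMANOVA of beta diversity uses sample covariates that are not named. Alpha diversity is compared by an unadjusted Mann-Whitney test.

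Two aims in Section IV depend on these analyses: obtaining variability data for sample size estimation (Aim 3), and Aim 4, to "evaluate the charges and costs of the NICU hospitalization and 2 months CA care" between the two groups.

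**The concern.** The GA range is wide, the arms are very small, and nothing in the design forces the arms to be alike on GA. Section VII.a.v places the first oral feeding attempts at about 33 to 34 weeks postmenstrual age, so a more immature infant spends longer in the unit before reaching that point. Duration of tube feeding and of hospitalisation are collected, and hospitalisation charges and costs are compared under Aim 4. A chance difference in GA therefore feeds directly into a comparison that the pilot sets out to make.

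For Aim 3 the issue is completeness. If the R01 is to adjust for GA, its sample size needs the residual SD or the GA-outcome correlation. The plan as written commits to neither, although the data to produce both will be in hand.

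**Working it through.** **Inputs.** From the documents: GA 22 to 33 weeks; 6 per arm (Section VI.c) or 10 per arm (abstract); 40% attrition; oral feeding from about 33 to 34 weeks postmenstrual age. Assumed, because the documents give no values: SD of GA 2.0 to 3.5 weeks (an even spread over 12 weeks gives 12/√12 = 3.46), and GA-outcome correlation ρ of 0.3, 0.5 or 0.7.

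**The plan's own figure.** 12 × (1 − 0.40) = 7.2, not the stated final 12. The 12 is reproduced only from the abstract's enrolment: 20 × 0.60 = 12. Results are therefore shown for 6 and 10 per arm, and for about 3.5 per arm in case 40% attrition does fall on 12 infants.

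**Chance imbalance in mean GA.** SE = SD × √(2/n); P(difference > 2 weeks) = 2 × [1 − Φ(2/SE)].

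| n per arm | SD 2.0 | SD 3.0 | SD 3.46 |
|---|---|---|---|
| 6 | SE 1.15, 8% | SE 1.73, 25% | SE 2.00, 32% |
| 10 | SE 0.89, 3% | SE 1.34, 14% | SE 1.55, 20% |
| 3.5 | SE 1.51, 19% | SE 2.27, 38% | SE 2.62, 45% |

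**What a GA difference means for stay.** Time from birth to oral feeding is about (33 to 34) − GA. That is 11 to 12 weeks for an infant born at 22 weeks and 0 to 1 week for one born at 33 weeks. Each week of difference in mean GA shifts this period by about a week, so a 2-week imbalance is about 14 days per infant with no treatment effect.

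**In outcome SDs, 6 per arm.** The 95% range of the GA-driven part of an arm difference is ±1.96 × ρ × √(2/6), which is ±0.34, ±0.57 and ±0.79 SD for ρ = 0.3, 0.5 and 0.7. GA's share of the chance variance is ρ²: 9%, 25% and 49%.

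**Effect on R01 size.** Residual SD = raw within-arm SD × √(1 − ρ²), a ratio of 0.95, 0.87 or 0.71. Sample size scales by 1 − ρ² = 0.91, 0.75 or 0.51. As an illustration (two-sided 0.05, 80% power, standardised effect 0.5), 63 per arm unadjusted becomes 58, 48 or 33.

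**Sampling error of the SD itself.** With 12 infants and 10 df, the chi-square 95% limits are 0.70 to 1.75 times the estimated SD, so planned N runs from 0.49 to 3.08 times.

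**Pilot precision, 6 per arm.** Unadjusted 95% half-width = 2.228 × √(2/6) = 1.29 SD. Adjusted = 2.262 × √[(1 − ρ²) × (2/6) × (1 + 1/8)] = 1.32, 1.20 or 0.99 SD for ρ = 0.3, 0.5 or 0.7, and 1.39 if ρ = 0.

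**Using the residual SD for an unadjusted R01.** Power = Φ[2.80 × √(1 − R²) − 1.96]. For R² = 30%, 50% and 70%, a nominal 80% becomes Φ(0.38) = 65%, Φ(0.02) = 51% and Φ(−0.425) = 34%.

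**The case against.** The strongest reply is that this is a feasibility pilot with no efficacy aim, and that adjusting 12 infants cannot make arm contrasts informative. That largely stands: half-widths stay near 1.0 to 1.3 SD, and at a correlation of 0.3 adjustment slightly widens the interval. It does not dispose of the point, because the cost comparison and the variability data are stated aims.

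Other replies also have force. Two assessments are partly aligned for age by design (34 weeks postmenstrual age and 2 months corrected age), although stay and NICU cost are not. Infants born earlier also receive the intervention for longer: from day 3 to 33-34 weeks is about 10.6 to 11.6 weeks at 22 weeks' gestation and at most 0.6 weeks at 33. A model with arm and GA as additive terms assumes the same arm effect at every GA, so the adjusted result belongs beside the unadjusted one and should not replace it.

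Three stronger readings are tempting, and the documents support none of them.

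- *GA is ignored altogether.* It is collected. Section IX allows for unspecified modelling, and the beta-diversity analysis uses covariates that could include it.
- *Arm differences would mostly reflect GA.* That needs ρ² above 50%. The documents give no such figure, and even ρ = 0.7 gives 49%.
- *The raw SD is wrong for R01 planning.* It is the correct input for an unadjusted R01 in the same population, and it errs towards too many infants for an adjusted one.

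**Conclusion.** The gap is real but bounded. Section IX assigns GA no role in the between-arm comparisons or the variability estimates, while eligibility is wide, allocation is unstratified, and the protocol's own feeding timeline ties pre-feeding stay to GA. The chance of a mean GA difference over 2 weeks is about 8% to 32% at 6 per arm and 3% to 20% at 10 per arm. These figures rest on an assumed GA SD of 2.0 to 3.5 weeks and a normal approximation. The step from pre-feeding stay to cost is an inference, since the documents give no daily cost.

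For the R01, the missing adjustment matters only if that trial will adjust for GA. Even then, the sampling error of an SD from 12 infants moves planned N by more than adjustment does at correlations up to 0.7. The case for the change is that it is cheap and uses a baseline value already collected.

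**What to change.** In Section IX:

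1. Report each continuous between-arm difference, in particular charges, costs and length of stay, with a 95% CI, both unadjusted and from a linear model with arm and GA at birth.
2. For Aim 3, report for each continuous outcome the raw within-arm SD, the GA-adjusted residual SD and the GA-outcome correlation, each with a CI.
3. State that the R01 will be sized with the SD that matches its planned analysis: the residual SD only if the R01 will adjust for GA, otherwise the raw SD.
4. Separately, reconcile the enrolment figures (12 or 20, and the attrition arithmetic), since the degrees of freedom depend on them.

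Randomisation, data collection and care do not change. The cost is a short addition to Section IX, a few lines of SAS, one degree of freedom in the adjusted model, and a slightly wider interval where the correlation is about 0.3 or less. If attrition leaves about 7 infants, the adjusted model has 4 df and the 95% limits for its residual SD are 0.60 to 2.87 times the estimate, so the CIs in item 2 should always accompany the estimates.
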